[name], OTD/S will coordinate this study by developing study materials, reporting adverse and serious events for all participants, recruiting, screening, and enrolling participants, as well as implementing quality control procedures, and assisting in data management and analysis. She will also develop materials for regulating bodies with assistance from study staff.

[name], MS, OTR/L will supervise and train staff during this study.

[name], OTD, MSCI, OTR/L will train staff and assist with assessments and statistical analysis performed for this project.

[name], MS will assist with data analysis for this study and maintain randomization codes.

Study Objectives

The objective of this feasibility study is to assess the acceptability and preliminary efficacy of a toileting intervention using an automated bidet system and training by an occupational therapy practitioner (OT) to reduce the amount of physical assistance required from caregivers.

Background & Study Rationale

[figure not shown]
Informal caregivers are unpaid family members or friends that provide over 30 billion hours of care annually for older adults (Chari, Engberg, Ray, & Mehrotra, 2015). They assist with activities of daily living (ADLs) and instrumental activities of daily living (IADLs), enabling their loved one to remain at home (Darragh et al., 2015; National Alliance for Caregiving and AARP Public Policy Institute, 2015). However, they often receive little to no training, especially for assisting with toileting, and are at an increased risk for physical injury, stress, and burnout (Darragh et al., 2015; National Alliance for Caregiving and AARP Public Policy Institute, 2015). This jeopardizes their loved ones' ability to age in place. Care recipients are more likely to be placed in a nursing home if they have difficulties completing ADLs such as toileting (Luppa et al., 2010).

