Informal caregivers report that assisting with toileting and managing incontinence are some of the most difficult ADLs (Darragh et al., 2015; King, Holliday, & Andrews, 2018; National Alliance for Caregiving and AARP Public Policy Institute, 2015). Informal caregivers with low self-efficacy or beliefs about their ability to assist with toileting tasks are at risk of experiencing depression or burnout (Bandura, 1982; Gilliam & Steffen, 2006; Grano, Lucidi, & Violani, 2017). Thus, a potential solution is an automated bidet system, a toilet seat with built-in cleaning features, to replace physical support provided by a caregiver for toileting. Automated bidet systems have been shown to reduce caregivers' use of non-neutral postures by 15% and severe trunk flexion by 32% (King et al., 2019). In another study, participants reported an increase in competence, adaptability, and self-esteem after using an automated bidet system compared to their regular toileting routine (Yachnin, Gharib, Jutai, & Finestone, 2017). Automated bidet systems have the potential to increase caregivers' self-efficacy, increase caregivers' satisfaction, reduce the amount of physical assistance needed for toileting, and decrease caregivers' risk for injury when assisting with toileting.

Study Design

In this randomized waitlist control feasibility study, ten informal caregivers and care recipient dyads will be recruited to the study and randomly assigned to either the treatment group or the waitlist control group. The treatment group will participate in the intervention immediately, receiving the automated bidet system and training, while the control group waits to receive the automated bidet. After completion of this phase, control participants will be provided with the automated bidet system and subsequent training. Outcome measures will be collected at pretest and posttest (30 days post-intervention for the treatment group or 30 days post-enrollment for the control group), and at follow-up for the waitlist control group (30 days post-installation). Assessments will be used to evaluate the feasibility of the feasibility, acceptability, and preliminary efficacy of this OT intervention to reduce the amount of assistance needed from caregivers. Overview of the study's major steps is shown in Figure 1.

Figure 1: Study Flow Diagram

Participants

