Ten informal caregivers will be recruited to participate in this study from a study registry, clinicians, exercise groups, and word of mouth in St. Louis, Missouri.

Informal caregivers will be contacted by phone and screened for eligibility. Caregivers will be eligible for this study if they: (1) provide unpaid care and lived with a care recipient aged 55

years or older; (2) have assisted with toileting for at least 6 months; (3) do not have an automated bidet; (4) have a working toilet and bathroom outlet; and (5) their care recipient is willing to participate. Participants will be excluded if they score a 10 or above on the Short Blessed Test, indicating a possible cognitive impairment.

Informed Consent

Written informed consent to participate in the study will be obtained before any assessments are conducted. If eligible, an occupational therapist (OT) will schedule a time to obtain consent at the potential participant's home. All elements of consent will be reviewed with caregivers prior to enrolling in the study, including the purpose of the study, risks, benefits, alternatives to the study, how confidentiality will be maintained, the PI's contact information, no consequences to withdrawal, and how study results will be shared. Participants will be given a copy of the signed consent for their records.

A written waiver of consent/exempt information sheet will be presented in person to all care recipients at the initial interview prior to administering the IHOPE-Assist. The OT will review the exempt information sheet with the care recipient during the consent visit in a private setting, including the purpose of the study, study procedures, and how confidentiality will be maintained. If the care recipient does not want to participate in the performance-based component of the evaluation, which includes toileting activities normally done in the home with the assistance of a caregiver, then the caregiver and care recipient will not be enrolled in the research study.

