Caregivers will be randomized using a 1:1 ratio by gender with a web-based randomization tool, Research Electronic Data Capture system (REDCap) after signing the consent (Harris et al., 2009). Randomization sequence concealment will be achieved by the Research Electronic Data Capture (REDCap) system (Harris et al., 2009).

Data Collection

Data will be collected at pretest and posttest (30 days post-intervention for the treatment group or 30 days post-enrollment for the control group), for the caregiver and care recipient in the participants' homes. Caregivers in the waitlist control group will also complete assessments at follow-up (30 days post-installation).

Covariate Assessments to be collected during the initial screening from the caregiver:

Demographics. Caregivers will be asked basic demographic information that includes birthdate, gender, marital status, ethnicity, income, years of education, years of caregiving, relation to care recipient, diagnosis of care recipient, and hours of caregiving provided per week.

Short Blessed Test (SBT). The SBT is a six-item measure that will be used to assess the caregiver's cognition, memory, and orientation as a screening tool prior to enrolling in the study (Katzman et al., 1983). The SBT has good validity. The score for each item is calculated based on the number of errors and a weighting factor; these scores are combined to calculate the total score. Total scores range from 0-28; higher scores indicate more cognitive impairment. Informal caregivers who score 10 or above will not be eligible for the study as that indicates impairments consistent with dementia.

Primary endpoint assessments to be completed by the caregiver throughout the study:

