In-Home Occupational Performance Evaluation for Providing Assistance (I-HOPE Assist). The I-HOPE Assist is a reliable and valid assessment which measures caregivers' self-reported satisfaction and performance, impact of environmental barriers, and self-efficacy for assistance with 43 specific daily activities (Keglovits, Somerville, & Stark, 2015). Caregivers use activity cards to identify the top 10 caregiving activities which are difficult or worrisome for them, one of which must be toileting. Next, they provide self-ratings of their performance, satisfaction with performance and self-efficacy for those activities on a scale of 0 to 5, with higher scores indicating better performance, satisfaction, and self-efficacy. For self-care and transfers for toileting, the OT will also record barriers to performance and rate the impact of the barrier on the caregiver's performance, yielding scores of barrier severity. This assessment will be used to measure changes in caregiver performance, satisfaction, and self-efficacy for providing assistance with toileting to evaluate the effects of the automated bidet system intervention on caregiver outcomes.

Process Evaluation. During the final study visit, caregivers will complete an 8-item process evaluation to assess the feasibility of the toileting intervention using an automated bidet system. Caregivers will rate how much they thought the automated bidet: (1) made assisting with toileting easier, (2) improved their confidence, and (3) addressed their concerns for assisting the care recipient with toileting. Caregivers will rate agreement with statements about the appearance, ease of use, and training and whether they will continue to use the automated bidet after the study on a scale of 0 (strongly disagree) to 4 (strongly agree), with higher scores indicating greater acceptance of the intervention. Caregivers will also complete a qualitative

interview to determine whether the number and length of visits were sufficient.

Statistical Analyses

Descriptive statistics will be used to examine demographic characteristics and feasibility outcomes. A Wilcoxon-signed rank test will be used to examine secondary outcomes to compare groups. Qualitative interviews will be analyzed using a grounded theory approach and constant comparative analysis.

Potential Benefits, Risks, and Alternatives

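### Must the plan say whether the comparison of arms takes account of gender, given that caregivers are randomised by gender?

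*Combined protocol and SAP*

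**What the plan says.** The Randomization section reads "Caregivers will be randomized using a 1:1 ratio by gender with a web-based randomization tool". I take this as randomisation stratified by caregiver gender; no block size is given. The Study Design section sets the size: "ten informal caregivers and care recipient dyads will be recruited to the study and randomly assigned to either the treatment group or the waitlist control".

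Gender is one of the demographic items listed in the Data Collection section under the line "Covariate Assessments to be collected during the initial screening from the caregiver", but no analytic use is stated for it. The quantitative part of Statistical Analyses is two sentences: "Descriptive statistics will be used to examine demographic characteristics and feasibility outcomes" and "A Wilcoxon-signed rank test will be used to examine secondary outcomes to compare groups". Neither mentions strata, adjustment, or a decision to leave gender out.

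The synopsis table gives recruitment as complete. Under Organizational Structure and Responsibilities, a team member "will assist with data analysis for this study and maintain randomization codes".

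**The concern.** The usual advice is to reflect in the analysis any factor used to restrict the randomisation. If gender predicts change, balancing on it makes the arms more alike than simple randomisation would. A test that ignores this counts the gender difference as noise, becomes conservative and loses power.

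With ten caregivers there is a second worry. An odd split, such as 9/1 or 7/3, cannot be balanced exactly. The unrestricted comparison then depends partly on which arm receives the extra caregiver of the rarer gender.

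Finally, a choice left open could be made after the data are seen, and at this size it could move a p-value across a conventional threshold.

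**Working it through.** The plan states no power, alpha, SD or effect size, so it has no figure to reproduce. The check asks what is lost under each choice.

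**Inputs from the documents.** Ten caregivers, 1:1 by gender. I-HOPE Assist outcomes are "self-ratings of their performance, satisfaction with performance and self-efficacy for those activities on a scale of 0 to 5".

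**Assumptions.** The compared scores are pre-to-post changes in those ratings. Changes are normal with SD 1, either untied or rounded to whole points. The treatment effect is 2 SD, the test two-sided at 5%, and allocation is in blocks of 2 within gender unless stated. The gender split and the gender effect on change are varied. A constant gender difference in rating level cancels in change scores, so only a difference in change matters.

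**Step 1: tests compared.** Both are exact tests on the rank sum. The unrestricted test uses all C(10,5) = 252 assignments, so its smallest two-sided p is 2/252 = 0.008. The within-gender test reassigns arms only inside each gender:

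- 8/2: C(8,4) × C(2,1) = 70 × 2 = 140 assignments, smallest p 2/140 = 0.014
- 6/4: C(6,3) × C(4,2) = 20 × 6 = 120 assignments, smallest p 2/120 = 0.017

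Either test can reach 5%.

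**Step 2: validity.** Type I error was simulated over splits from 9/1 to 5/5, blocks of 2 or 4, untied or whole-point scores, gender effects of 0, 1 or 2 SD, and enrolment drift of 0 or 2 SD. It was 0.3–3.7% for the unrestricted test and 0.7–4.8% within gender. Ignoring gender does not inflate false positives.

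**Step 3: power, averaged over allocations** (%, unrestricted vs within gender):

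| Split | No gender effect, untied | No gender effect, whole-point | 1 SD, untied | 1 SD, whole-point |
|---|---|---|---|---|
| 9/1 | 69 vs 66 | 64 vs 60 | 65 vs 65 | 60 vs 60 |
| 8/2 | 68 vs 66 | 63 vs 54 | 60 vs 65 | 55 vs 54 |
| 7/3 | 69 vs 70 | 63 vs 63 | 60 vs 69 | 55 vs 62 |
| 6/4 | 68 vs 71 | 63 vs 61 | 57 vs 70 | 52 vs 61 |
| 5/5 | 68 vs 69 | 63 vs 63 | 57 vs 67 | 52 vs 63 |

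In the last three rows at 1 SD, the gain from using gender runs from 62 − 55 = 7 to 70 − 57 = 13 points. At 8/2 with whole-point scores and no gender effect, there is a loss of 63 − 54 = 9.

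**Step 4: a smaller gender effect.** At 0.5 SD the figures for 7/3, 6/4 and 5/5 are 65 vs 69, 65 vs 71 and 66 vs 69 untied, and 61 vs 63, 58 vs 59 and 61 vs 64 whole-point: gains of 1 to 6 points. At 8/2 whole-point there is a loss of about 5 to 7 points (59 vs 54 and 62 vs 55 in two separate simulations).

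**Step 5: block size.** With blocks of 4, two caregivers of the rarer gender take the first two places of a block. Two of its six arrangements put them in the same arm, a chance of 2/6 = 1/3, and they then add nothing to a within-gender comparison. Power at 8/2 with whole-point scores is 63 vs 46 with no gender effect (loss 17) and 56 vs 46 at 1 SD (loss 10).

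**Step 6: odd splits.** At 9/1 the lone caregiver shifts the difference in arm means by 1 SD × (1/5 − 0/5) = 0.2 SD; at 7/3 the shift is 1 SD × (2/5 − 1/5) = 0.2 SD. Unrestricted power at 9/1, if the rarer gender changes more, is 54% with that caregiver in the control arm and 73% in the treated arm, against 66% within gender either way.

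**The case for a change.** The best argument for a change is that a sentence costs almost nothing. Gender is collected and the team holds the codes. The sentence naming the group test needs attention anyway, because a signed-rank test is for paired data and these are independent arms; whoever replaces it must choose with or without gender, and a choice fixed in advance cannot be steered by the result. Preliminary efficacy is a stated objective, so the comparison will be read.

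Part of this stands. The omission is real, the 7 to 13 point gains are correct under their assumptions, and Step 6 shows that an unlucky allocation can matter. The paired test deserves correction on its own account.

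It does not follow that the gender clause is a defect. Using a factor for balance only is legitimate, and here it leaves the test valid. A firm instruction to test within gender could be the worse choice, as the 8/2 figures show. Recruitment is complete, so the team can read the actual split. The demographic description already planned is the natural place to show it by arm. With no alpha or decision rule, no conclusion of the trial hangs on either p-value.

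**Conclusion.** The concern does not call for a change to the plan. The silence on gender is a gap that analysts can fill sensibly: either a within-gender or an unrestricted exact comparison is defensible, provided the report says which was used.

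What is at stake is power alone. It ranges from a gain of about 13 points for the within-gender test (6/4, untied, 1 SD gender effect) to a loss of about 17 (8/2, whole-point, blocks of 4, no gender effect). Gains of 7 points or more appear only with a gender effect near 1 SD and at least three caregivers of the rarer gender. For a smaller treatment effect the choice hardly matters: at 1 SD for both treatment and gender, whole-point, power is 13 vs 12% at 8/2 and 12 vs 17% at 6/4.

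All of this rests on assumed splits, effect sizes, SD and a 5% level, none of which the documents give, and on reading the compared outcomes as changes in the I-HOPE Assist ratings.

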| Intervention(s) | 
Study arm 1: Treatment
 
 Participants assigned to this group will receive an automated bidet (TOTO Washlet S300e with remote control) and an occupational therapy intervention over 2-3 in-home visits. During the first intervention visit, a licensed contractor will install the bidets in participants' homes. The OT will then educate and train the caregiver and care recipient to successfully use the bidet, and make any modifications to the remote as needed. Throughout the intervention, the OT will use motivational enhancement strategies. The OT will make minor modifications to the remote as needed. A second intervention visit will occur 1-2 weeks post-installation to address any new difficulties. Check-in phone calls will be offered to the caregiver and care recipient if needed. 
Study arm 2: Waitlist Control
 
 Caregivers will wait for 30 days and then will be offered the intervention. No intervention. |
| Key Inclusion and Exclusion Criteria | 
Inclusion criteria:
 
(1) provided unpaid care and lived with a care recipient aged 55 years or older
 
(2) assisted with toileting for at least 6 months
 
(3) did not have an automated bidet
 
(4) had a working toilet and bathroom outlet, and (5) their care recipient was willing to participate
 
Exclusion criteria:
 
(1) Caregivers scoring 10 or above on the Short Blessed Test, indicating possible cognitive impairment
 |
| Study Type | Randomized waitlist control feasibility study |
| Date of First Enrollment | December 20, 2016 |
| Target Sample Size | 10 |
| Recruitment Status | Complete |
| Primary Outcome(s) | 
 Number of participants recruited Number of caregivers retained Ability to install the automated bidets, including any modifications needed Caregivers' or care recipients' ability to operate the bidet Acceptability Preliminary efficacy: reduction of physical barriers to toileting Preliminary efficacy: Performance Preliminary efficacy: Satisfaction Preliminary efficacy: Self-efficacy Adverse events |

Organizational Structure and Responsibilities

[name]., OTR/L FAOTA is the principal investigator and will manage and oversee all aspects of this project. She will ensure compliance with quality-assurance requirements as stipulated by human subjects, and submit appropriate materials as needed throughout the study.

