All study staff have undergone IRB training. In addition, all staff members have participated in cultural competence training and are trained to interview older adults. All study documents will be available in multiple formats, are developed in 12-point Arial font, and are written in plain language. If a participant needs to be re-consented at any point during the study, the study staff will visit the person in home and repeat the consent process. All signed consents will be stored in the office of the PI under double locks.

Study Intervention

After randomization, the OT will contact all participants to inform them of their group allocation (Treatment or Control). A home visit will be scheduled as soon as possible for the participants in the treatment group. The waitlist control group will wait 30 days before receiving the automated bidet system and subsequent training.

Intervention Procedures. A visit will be scheduled after the pretest visit for installation and training on the automated bidet system (TOTO Washlet S300e with remote control). During the first intervention visit, the licensed contractor will install the automated bidet. After installation, the OT will provide training to the caregiver and care recipient on using the automated bidet system and will make modifications to the remote as needed. A second intervention visit will be completed 1-2 weeks post-installation to address any new difficulties with using the automated bidet system. During the intervention visits, the OT will utilize motivational enhancement and active practice, and provide education on programming the remote control for the care recipient's desired temperature, water pressure, and wand position to increase independence with toilet hygiene. The caregiver will be instructed to contact the OT if they have any questions.

Control Group Procedures. The procedures for the waitlist control group will be the same as above. During the initial 30 days, participants randomized to the control group will wait to receive the automated bidet. After completing assessments after the first 30 days, they will receive the automated bidet and follow the same intervention procedures described above.

Randomization

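### Could the pretest I-HOPE Assist be taken after the caregiver already knows the arm?

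*Combined protocol and SAP*

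**What the plan says.** Five sections bear on the order of events.

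- **Randomization:** caregivers are allocated 1:1 by gender with the "Research Electronic Data Capture system (REDCap) after signing the consent".
- **Study Intervention:** "After randomization, the OT will contact all participants to inform them of their group allocation (Treatment or Control"). An early home visit is then arranged for the treatment arm, while controls wait 30 days.
- **Study Intervention, Intervention Procedures:** "A visit will be scheduled after the pretest visit for installation and training on the automated bidet system".
- **Informed Consent:** consent precedes every assessment. The care recipient receives the information sheet "at the initial interview prior to administering the IHOPE-Assist", and the therapist goes through it at the consent visit.
- **Data Collection, I-HOPE Assist:** caregivers rate their own performance, satisfaction and self-efficacy from 0 to 5. For toileting, "the OT will also record barriers to performance and rate the impact of the barrier". On use, the section says: "This assessment will be used to measure changes in caregiver performance, satisfaction, and self-efficacy for providing assistance with toileting".

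The Study Design section adds that an overview of the study's "major steps is shown in Figure 1". That figure is not in the text available here. The summary table gives "Recruitment Status | Complete" and a target of 10.

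**The concern.** Read alone, the Randomization sentence is satisfied once consent is signed, and consent comes before any assessment. Allocation could then precede the pretest, and the therapist could tell the caregiver the arm before the pretest was done. The rule that installation follows the pretest keeps the baseline free of the bidet itself, but not of knowledge of the arm.

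All the I-HOPE Assist scores are subjective, and the plan describes no blinding of caregiver or rater. A caregiver who knows that the bidet is coming now, or only in 30 days, might rate toileting differently. A therapist who knows the arm might rate barriers differently. Randomization does not remove such a difference, because it arises after allocation, and it would pass straight into the change scores for preliminary efficacy. Ratings at posttest are made with the arm known whatever the plan says. A known-arm baseline, by contrast, can be avoided at almost no cost.

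**Working it through.** The plan gives no figure to reproduce on this point. The main check is one of order.

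**1. What is stated.** The text fixes four orderings:

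- consent before assessments (Informed Consent);
- consent before randomization (Randomization);
- randomization before disclosure (Study Intervention);
- pretest before installation (Intervention Procedures).

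**2. Which sequences satisfy all four.**

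- A: consent, pretest, randomization, disclosure, installation.
- B: consent, randomization, disclosure, pretest, installation.
- C: consent, randomization, pretest, disclosure, installation.

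Only B has the caregiver rate the baseline with the arm known. On these four sentences alone, B is not excluded.

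**3. What the rest of the text adds.**

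- Informed Consent describes the information sheet as given at the initial interview, ahead of the I-HOPE Assist, and reviewed at the consent visit. That places the pretest at or close to the consent visit.
- Data Collection has the pretest done in the home for both arms. After disclosure, Study Intervention arranges an early home visit for the treatment arm only. Under B, a control dyad would also need a home visit at that stage, and none is provided. Under A or C it needs none.
- The control arm's posttest falls 30 days after enrollment. That is a sensible pre-post interval if the pretest is done at about enrollment.

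B therefore fits the text poorly, while A fits it without strain. C also protects the self-ratings, and it protects the barrier ratings if the therapist has not yet seen the allocation.

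**4. Size if B had happened.** Assume 5 per arm and an analysis of change on the 0–5 scale.

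- One treated caregiver moved by 1 point: 1/5 = 0.2 points in the arm difference.
- All five moved by 1 point: 5 × 0.2 = 1.0 point, and 1.0/5 = 20% of the scale.
- SE of the arm difference = SD × √(2/5). For an assumed SD of 0.8 this is 0.51, and for 1.5 it is 0.95. An average shift of 0.5 points is then 0.5/0.51 ≈ 0.99 SE or 0.5/0.95 ≈ 0.53 SE.
- The plan names a signed-rank test and states no alpha. On five pre-post pairs its smallest two-sided p is 2/2⁵ = 0.0625, so at a 5% level it could not reject at all. Any harm would be to the estimate.
- A comparison of posttest scores alone would be unaffected.

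**The case for a change.** The strongest case for acting is that a protocol should not leave this to inference. The supporting sentences allow the right order but do not require it. The text never equates the pretest visit with the consent visit, and enrollment depends on the care recipient's willingness to take part, not on a completed pretest. The same title, OT, is used for the person who discloses the arm and the person who rates barriers. One sentence would close the gap, and a line per dyad in the report would show what was done.

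It stands that the rule is not written in words in the readable text. Three things weaken the rest.

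- Signed consent is not the only condition for entry. The Participants and Informed Consent sections also require the care recipient's willingness, and a Short Blessed Test score of 10 or above excludes the caregiver. Signing is the earliest point for allocation, not a trigger.
- A flow diagram of the major steps is where this order would normally appear. Its absence from the text read here cannot be counted as an omission from the plan.
- The error rates that can be attached to the problem do not describe this plan. An exact rank-sum test on 5 against 5 has size 8/252 = 3.2%. In simulation with normal scores, an assumed 0.5-point shift raises this to 4.9–9.6%, and a 1-point shift to 10–31%. With whole-point ratings at the same cutoff, the figures are 3.4–5.2% and 7.8–20.6%, from a base of 1.5–2.1%. The shifts, the SDs and the test itself are all assumed.

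**Conclusion.** No change is needed. What remains is an ordering rule not spelled out in the readable text, which staff following the plan on its natural reading would apply correctly. That conclusion rests on inference from the Informed Consent, Study Intervention and Data Collection sections. It would weaken if Figure 1 showed allocation and disclosure ahead of the pretest.

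The possible size is not trivial on paper: 0.2 points per affected caregiver, up to 1.0 point if all five treated caregivers moved by 1 point. It arises only if a baseline was taken after disclosure, and nothing in the documents suggests that one was. Recruitment is complete, so rewording the Randomization section now would protect no baseline. Reporting the order dyad by dyad would matter only if such a departure had occurred. In a ten-dyad feasibility study that claims only preliminary efficacy, and whose posttest ratings are made with the arm known in any case, this is a gap in wording, not a defect in the design.

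### The only hypothesis test in the plan, a Wilcoxon signed-rank test, is a paired test assigned to compare two independent randomized arms; no between-arm test is named.

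*Combined protocol and SAP*

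**What the plan says.** The quantitative plan in the Statistical Analyses section is two sentences. The first is descriptive: "Descriptive statistics will be used to examine demographic characteristics and feasibility outcomes". The second is the only one that names a hypothesis test: "A Wilcoxon-signed rank test will be used to examine secondary outcomes to compare groups".

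The Study Design section describes the groups being compared: "ten informal caregivers and care recipient dyads will be recruited to the study and randomly assigned to either the treatment group", or to a waitlist control group. The Randomization section adds: "Caregivers will be randomized using a 1:1 ratio by gender". Neither section describes matching one treated caregiver to one waitlist caregiver.

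Under Control Group Procedures, the waitlist arm is untreated for the first period: "During the initial 30 days, participants randomized to the control group will wait to receive the automated bidet". Both arms are assessed at pretest and posttest, with posttest set at "30 days post-intervention for the treatment group or 30 days post-enrollment for the control group". The waitlist arm has a further assessment 30 days after installation.

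Three of the four efficacy outcomes are I-HOPE Assist self-ratings "on a scale of 0 to 5, with higher scores indicating better performance, satisfaction, and self-efficacy". The fourth is barrier severity, rated by the occupational therapist. The synopsis table lists all four as primary outcomes, and Data Collection introduces the I-HOPE Assist under a primary endpoint heading. The test sentence, however, applies to secondary outcomes, and no outcome in the document carries that label.

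**The concern.** A signed-rank test takes one difference per pair and asks whether those differences centre on zero. Two separately randomized arms supply no such pairs, and stratifying the allocation by gender does not create them. The named test and its stated purpose are therefore incompatible.

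Preliminary efficacy is part of the stated objective, and the waitlist arm exists to show what happens to the ratings without the bidet and training. An analyst following the sentence has three options, and none is a valid comparison of the arms:

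- test change within one arm;
- match treated to waitlist caregivers arbitrarily;
- pool everyone's change.

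The first two can hide a real difference. The third can present change shared by both arms as an effect. Because the plan does not say which is meant, neither direction of error is the expected one.

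**Working it through.** **Plan's own figure.** There is none to reproduce. The target of 10 is given without a calculation, and no significance level, sidedness, power or effect size is stated.

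**Inputs.** From the documents: 10 caregivers, 1:1 allocation, pretest and posttest in both arms, ratings from 0 to 5. Assumed: 5 per arm, two-sided 0.05, exact tests and, for the simulations, normally distributed change scores.

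**1. Smallest attainable two-sided p-values**

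| Test | Formula | Result |
|---|---|---|
| Signed-rank, 5 pairs | 2/2^5 = 2/32 | 0.0625 |
| Signed-rank, 6 pairs | 2/2^6 = 2/64 | 0.031 |
| Signed-rank, 10 pairs | 2/2^10 = 2/1024 | 0.002 |
| Rank-sum, 5 v 5, no ties | 2/C(10,5) = 2/252 | 0.0079 |
| Rank-sum, 4 v 4, no ties | 2/C(8,4) = 2/70 | 0.029 |

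With five pairs, an exact signed-rank test therefore rejects 0% of the time at any effect size.

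The method of computing p also matters. For five untied changes in the same direction, the uncorrected normal approximation is z = (15 − 7.5)/√(5·6·11/24) = 7.5/3.708 = 2.02, p = 0.043. With continuity correction, z = 7.0/3.708 = 1.89, p = 0.059. Significance would then turn on an option the plan does not state.

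**2. Worked examples, whole-point changes**

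| Treated | Waitlist | Signed-rank | Exact rank-sum |
|---|---|---|---|
| 3,3,2,2,2 | 1,1,0,0,0 | 0.0625 within the treated arm and under all 120 pairings | 0.0079 |
| 3,2,2,1,1 | 1,1,0,0,0 | between arms: 0.0625, 0.125 or 0.25, depending on the pairing | 0.048 |
| 1,1,2,2,1 | 1,1,2,2,1 | 0.002, all 10 pooled | 1.0 |

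In the second row, matching a treated change of 1 to a waitlist change of 1 gives a zero difference, which is dropped. Five, four or three non-zero differences remain, so p is 2/32, 2/16 or 2/8. The rank-sum value counts the arrangements as extreme as the one observed: 12/252 = 0.048.

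**3. Simulated rejection with no intervention effect, all 10 changes pooled**

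| Change common to both arms | Continuous scores | Rounded to half SDs | Rounded to whole SDs |
|---|---|---|---|
| 0 | 4.9% | 3.2% | 1.6% |
| 0.5 SD | 28.2% | 23.0% | 14.9% |
| 1.0 SD | 78.4% | 73.5% | 62.8% |

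For smaller shared changes of 0.1 and 0.25 SD the rate is about 6% and 11%. At 0.5 and 1.0 SD the rank-sum test stays at 3.1% and 3.2% with continuous scores, and at 2.4% for both with whole-SD rounding.

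**4. Power of the rank-sum test, 5 v 5.** At between-arm differences of 1 and 2 SD, power is 20.6% and 67.6% with continuous scores, and 16.5% and 62.0% with whole-SD rounding. It is a valid test here but a weak one.

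**The case against.** The strongest reply is about proportion. This is a 10-dyad feasibility study with no stated hypothesis or decision rule attached to the test, and signed-rank could easily be a slip for rank-sum. That limits the harm to the preliminary-efficacy comparison, but the sentence would still have to change.

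A second reply is that pooling all 10 changes compares no groups, so the sentence does not really invite it, and that the documents give no basis for a shared change of 0.5 or 1.0 SD. This is fair. The pooled rates are the weaker illustration, and they are modest when the shared change is small.

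Third, the waitlist follow-up gives a legitimate paired use. Change from before to after the intervention exists for all 10 caregivers, taking posttest to follow-up in the waitlist arm, and the floor is then 0.002. That is true, but the analysis is uncontrolled and does not compare the arms.

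Fourth, the 0% figure needs exactly five pairs and an exact test. A 6:4 split is possible, and six pairs can reach 0.031. This also stands, and the figure is conditional on those assumptions. None of these points supplies a valid between-arm test.

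**Conclusion.** The concern holds. The one inferential rule in the plan names a paired test for a comparison of independent arms, and each charitable reading still requires a correction. If rank-sum was meant, the test name is wrong. If within-caregiver change was meant, the stated purpose is wrong and the randomized contrast has no test.

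At 5 per arm with exact two-sided tests at 0.05, the consequence ranges from no possibility of significance (five pairs) to false-positive rates well above 5% (all changes pooled, with a material shared change). The feasibility outcomes are unaffected. Even the correct test can support only an exploratory statement at this sample size. The sentence must still be fixed, because it is the plan's only rule for its efficacy outcomes and correcting it costs almost nothing.

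**What to change.** If a between-arm comparison is intended, replace the sentence with:

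> Change from pretest to posttest in barrier severity, performance, satisfaction and self-efficacy will be compared between arms by an exact two-sided Wilcoxon rank-sum (Mann-Whitney) test with midranks for ties, reported with an effect estimate and interval, and interpreted as exploratory.

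A permutation test within gender strata is an acceptable alternative that follows the allocation more closely; name one of the two.

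Keep the signed-rank test, if wanted, as a supportive within-caregiver analysis. State which assessments form each pair, and label it as uncontrolled and open to drift and repeat-rating effects. If only within-caregiver change was ever intended, remove the reference to comparing groups and say that the randomized contrast will be described without a test.

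Two clarifications belong in the same edit:

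- State that the contrast is the bidet-plus-training package against waiting, and that posttest is timed from intervention in one arm and from enrollment in the other.
- Reconcile the secondary label in Statistical Analyses with the primary labels in the synopsis table and Data Collection. The choice of label is the investigators'.

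The cost is analysis wording only, with no new data, visits or participants. Because the synopsis marks recruitment as complete, date the change, disclose that it was made after recruitment, and state whether outcome data had been seen.
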